APPENDIX A

Additional Details Pertaining to Study Design for Clinical Trials

Appendix A must be completed for investigator/student initiated research projects that require review by the convened board. For example, studies that use investigational test articles, that present more than minimal risk to subjects, or that involve prisoners, must be reviewed by the convened board.

Topical (*Intra-Articular*) Tranexamic Acid and Transfusion Rates Following Hip ~~Hip Arthroplasty~~

Note that for studies requiring review by the convened board the full board application must be completed, data safety monitoring must be addressed (e.g. by completion of Appendix B to the main application) and the Investigator Brochure and /or package insert must also be submitted if available.

1. *For a clinical trial (e.g. a Phase I, II or III study), the use of the intervention must be fully described e.g., the treatment regimen for use of drugs, placebo, medical device etc. Also include plans for receipt of test article, storage, dispensing and reconciliation.* : The intervention, the application of either 1 gram of tranexamic acid mixed with normal saline (0.9% NaCl) for a total volume of 50 cc or 50 cc of normal saline (0.9% NaCl) placebo, will occur intra-operatively just prior to wound closure. One half, or 25 cc, of either the study drug or the saline placebo will be applied intra-articularly. The second half, or 25 cc, will be applied under the fascia. When applying either the study drug or saline placebo, the resident performing the case or the attending surgeon will attempt to coat all exposed tissues with a thin layer of the aqueous solution. This is a one-time dose. Provision of the study drug (Tranexamic acid or saline placebo) will be provided by the hospital pharmacy. The pharmacy is responsible for the storing and dispensing the study drug.
2. *Provide a description of known adverse events due to the intervention and the plan to deal with such adverse events (e.g. dose reduction, removal of device, removal from trial.)*: The package insert for Tranexamic acid provides a section on known adverse reactions with injection of the drug. Gastrointestinal disturbances (nausea, vomiting, diarrhea), allergic dermatitis, giddiness, and hypotension have been reported occasionally with intravenous injection. Worldwide post marketing reports include thromboembolic events (e.g. deep vein thrombosis, pulmonary embolism, cerebral thrombosis, acute renal cortical necrosis, and central retinal artery and vein obstruction) have been rarely reported. Convulsion, chromatopsia, and visual impairment have also been reported. However, due to the spontaneous nature of reporting of medical events and lack of controls the actual incidence and causal relationship of the drug and event cannot be determined.

There is no information regarding adverse reactions with topical use of tranexamic acid in the package insert. A review of the literature revealed a Cochrane review on topical application of tranexamic acid for the reduction of bleeding. Ker et al. reported topical use of the drug was not

Topical (*Intra-Articular*) Tranexamic Acid and Transfusion Rates Following Hip ~~Hemiarthroplasty~~

associated with an increased rate of complications. Topical use of the drug was associated with a relative risk of 0.28 (95% CI, 0.06-1.34; P = 0.11) for mortality, 0.33 (95% CI, 0.04-3.08; P = 0.33) for myocardial infarction, 0.33 (95% CI, 0.01-7.96; P = 0.49) for stroke, 0.69 (95% CI, 0.31-1.57; P = 0.38) for DVT, and 0.52 (95% CI, 0.09-3.15; P = 0.48) for pulmonary embolism [6]. These rates were comprised from 29 randomized control trials with 2,612 patients.

In the event an adverse event occurs, the surgeon and patient will be un-blinded and the patient will be treated according to standard medical practices. Adverse events will include mortality and thromboembolic events (pulmonary embolism, deep vein thrombosis, myocardial infarction, cerebrovascular accident, acute renal cortical necrosis, central retinal artery or vein obstruction).

3. *Describe circumstances that may lead to a subject being removed from the trial by the PI, e.g. due to failure to follow study procedures, and the process for doing so:* Since the study involves a one time intra-operative dose of tranexamic acid or placebo, there is no specific study procedure that the patient will be required to follow. Patients will be removed from the trial if the assigned intervention is not available to the operating room staff prior to wound closure.
4. *Describe any stopping rules for the study:* The study will be stopped if an increase in the rate of mortality, pulmonary embolism, deep vein thrombosis, myocardial infarction, cerebrovascular accident, acute renal cortical necrosis, or central retinal artery or vein obstruction is observed. These are considered to be rare events following elective hip hemiarthroplasty. The study stopping rules for these events are described in the following table:

Adverse Event	Stopping Criteria	Reference(s)
Mortality	The 30-day mortality rate following hip hemiarthroplasty has been reported to range from 2.4% to 10.1%. Assuming a conservative estimate of 6.25% mortality and a sample size of 102 patients, we would expect to see 6-7 patient deaths overall during our study period,	The 30-day mortality rate in patients undergoing hip arthroplasty for displaced hip fracture was 2.4% (186 of 7774). Parvizi J, Ereti MH, Lewallen DG. Thirty-day mortality following hip

	
which begins on the date of surgery and ends 4-6 weeks postoperatively. In each 51 patient subgroup, we would expect to see 3-4 patient deaths over the study period when applying this 6.25% mortality rate. If death occurs in 5 patients in the tranexamic acid subgroup (1 death above the expected), the study will be stopped and an inter-group assessment will occur (see below). If 4 or fewer patient deaths (3 to 4 patient deaths are expected based upon our conservative assessment of the literature) occur in the tranexamic acid subgroup, the study will be continued until completion.
 
It is possible that the placebo group will have a higher number of deaths due to chance, due to our conservative estimate of mortality rate (6.25%) for our study duration, or due to a protective effect from tranexamic acid. Mortality rates following hip hemiarthroplasty are variable. Topical use of tranexamic acid has been associated with a relative risk of 0.28 (95% CI, 0.06 to 1.34; $P = 0.11$) for mortality. If the placebo group has experienced a greater number of deaths than would be expected from our conservative estimate based upon the available literature ($n = 5$ or greater), we will continue the study.
 
If 5 patient deaths (1 above the expected) occur in the tranexamic acid subgroup and 4 or fewer patient deaths have occurred in the placebo subgroup, the study will be stopped.
 
If 5 patient deaths (1 above the expected) occur in the tranexamic acid subgroup and 5 or more deaths have already occurred in the placebo subgroup, we will continue the study. In this instance, the study will either continue to completion or be stopped if at any point the number of deaths in the tranexamic subgroup exceeds that of the control.
	
arthroplasty for acute fracture. J Bone Joint Surg Am. 2004 Sep;86-A(9):1983-8.
 
At one month, 359 out of 3,634 (9.9%) patients receiving a cemented hemiarthroplasty and 1,051 out of 10,362 (10.1%) patients receiving a cementless hemiarthroplasty had died.
 
 
The 90-day mortality rate of patients undergoing hip hemiarthroplasty was 9.8% in patients 65-84 years of age and 18.3% in patients ≥ 85 years of age
 
 
Topical use of the tranexamic acid is associated with relative risk of 0.28 (95% CI, 0.06 to 1.34; $P = 0.11$) for mortality.
 
 
The number of patients who experienced a symptomatic in-hospital pulmonary embolism in

Pulmonary Embolism	A 1.2% rate of in-hospital pulmonary embolism has been reported for patients undergoing total hip arthroplasty. A rate of	

	
1.1% to 1.3% has been reported at 90 days for patients who underwent hip hemiarthroplasty.
 
Assuming a conservative estimate of 1% for the rate pulmonary embolism in this patient population, we expect to see 0-1 patients develop a pulmonary embolism in the tranexamic acid subgroup (n = 51). The occurrence of pulmonary embolism in 2 patients (1 above the expected) in the tranexamic acid subgroup will be sufficient to stop the study for an inter-group assessment.
 
As with mortality, it is possible that the placebo subgroup will have a higher incidence of pulmonary embolism. If 2 patients (1 above the expected) in the tranexamic acid subgroup experience a pulmonary embolism and if 2 or more patients in the placebo group have already experienced a pulmonary embolism, we will continue the study. In this instance, the study will continue to completion or be stopped if at any point the number of patients with a pulmonary embolism in the tranexamic acid subgroup exceeds that of the control.
 
If 2 patients in the tranexamic acid subgroup experience a pulmonary embolism and 1 or fewer patients in the placebo subgroup have experienced a pulmonary embolism, the study will be stopped.
	
patients undergoing total hip replacement was 37/3028 (1.2%). O'Reilly RF, Burgess IA, Zicat B. The prevalence of venous thromboembolism after hip and knee replacement surgery. MJA. 2005; 182: 154-159.
 
The 90-day incidence of pulmonary embolism in patients undergoing hip hemiarthroplasty was 1.3% (540/41,770) in patients 65-84 years old and 1.2% (422/35,321) in patients 85 years or older.
 

Deep Vein Thrombosis (DVT)	
Deep vein thrombosis is a complication following surgery that is highly dependent upon screening practices. When asymptomatic patients admitted to the hospital have been indiscriminately screened with ultrasound, deep vein thrombosis rates have ranged from 5.5% to 17.8%. Following total hip arthroplasty, a deep vein thrombosis rate of 8.9% has been reported in patients within 7 days postoperatively with universal screening.
 
Treatment for deep vein thrombosis involves a protracted course of pharmacologic anticoagulation, which is associated with
	
The prevalence of asymptomatic deep vein thrombosis on admission was 5.5% and reached 17.8% in patients above 80 years of age.
 
 
The number of patients developing

Topical (*Intra-Articular*) Tranexamic Acid and Transfusion Rates Following Hip Hemiarthroplasty

	
potentially lethal bleeding complications. Therefore, current standards of care require screening in symptomatic patients only, to prevent diagnosing and treating asymptomatic individuals with clinically insignificant DVTs. Though screening is limited to symptomatic individuals, the threshold for initiating screening amongst clinicians is variable. The decision to initiate screening is also susceptible to detection bias.
 
The rates of deep vein thrombosis following hip hemiarthroplasty have been reported to range from 1.1% to 1.3%. Since this diagnosis is so dependent upon variable screening practices and since we believe study inclusion may result in a lower clinical threshold for screening, we will assume a rate of 3% as a conservative estimate of the deep vein thrombosis rate in this patient population.
 
Assuming a conservative estimate of 3% for the rate of deep vein thrombosis in this patient population, we expect to see 1-2 patients develop a deep vein thrombosis in the tranexamic acid ($n = 51$) subgroup. The occurrence of deep vein thrombosis in 3 patients (1 above the expected) in the tranexamic acid subgroup will be sufficient to stop the study for inter-group assessment.
 
As with mortality, it is possible that the placebo subgroup will have a higher incidence of deep vein thrombosis. If 3 patients (1 above the expected) in the tranexamic acid subgroup experience a deep vein thrombosis and if 3 or more patients in the placebo group have experienced a deep vein thrombosis, we will continue the study. In this instance, the study will continue to completion or be stopped if at any point the number of patients with a deep vein thrombosis in the tranexamic acid subgroup exceeds that of the control.
 
If 3 patients in the tranexamic acid subgroup experience a deep vein thrombosis and 2 or
	
deep vein thrombosis within 7 days postoperatively was 263/3028 (8.9%) after total hip replacement. O'Reilly RF, Burgess IA, Zicat B. The prevalence of venous thromboembolism after hip and knee replacement surgery. MJA. 2005; 182: 154-159.
 
The 90-day incidence of deep vein thrombosis in patients undergoing hip hemiarthroplasty was 1.3% (537/41,770) in patients 65-84 years old and 1.1% (383/35,321) in patients 85 years or older. Jameson SS, Khan SK, Baker P, James P, Gray A, Reed MR, Deehan DJ. A national analysis of complications following hemiarthroplasty for hip fracture in older patients. QJM. 2012 May;105(5):455-60.

--	--	---

Topical (*Intra-Articular*) Tranexamic Acid and Transfusion Rates Following Hip Hemiarthroplasty

	
fewer patients in the placebo subgroup have experienced a deep vein thrombosis, the study will be stopped.
	
Myocardial Infarction	
The 30-day incidence of myocardial infarction following hip hemiarthroplasty has been reported to be 1.9% in patients 65-84 years of age (790 in 41,770 patients) and 3.1% in patients \geq 85 years of age (1101 in 35,321 patients).
 
Assuming a rate of 1.9% to 3.1% for myocardial infarction in this patient population, we would expect to see 1-2 patients in the tranexamic acid subgroup (n = 51) experience a myocardial infarction in the 4-6 week period following the surgical intervention. The occurrence of myocardial infarction in 3 patients (1 above the expected) in the tranexamic acid subgroup will be sufficient to stop the study for inter-group assessment.
 
As with mortality, it is possible that the placebo subgroup will have a higher incidence of myocardial infarction. If 3 patients (1 above the expected) in the tranexamic acid subgroup experience a myocardial infarction and if 3 or more patients in the placebo subgroup have experienced a myocardial infarction, we will continue the study. In this instance, the study will either continue to completion or be stopped if at any point the number of myocardial infarction in the tranexamic acid subgroup exceeds that of the control.
 
If 3 patients (1 above the expected) in the tranexamic acid subgroup experience a myocardial infarction and fewer than 3 patients in the placebo subgroup have experienced a myocardial infarction, the study will be stopped.
	
The 30 day incidence of myocardial infarction is 1.9% in patients 65-84 years of age and 3.1% in patients \geq 85 years of age.
 

Cerebrovascular Accident	
The 30-day incidence of cerebrovascular accident following hip hemiarthroplasty has been reported to range from 0.1% to 1.5%.
	
The 30 day incidence of stroke is 0.1% in patients 65-84 years of age and 0.1% in patients \geq 85 years of age.

(Stroke)	
Assuming an anticipated rate of 0.1% to 1.5%, we would expect 0-1 patients in the tranexamic acid subgroup (n = 51) to experience a cerebrovascular accident in the 4-6 week period following their surgical intervention. The occurrence of cerebrovascular accident in 2 patients in the tranexamic acid subgroup (1 event above the expected) will be sufficient to stop the study for an inter-group assessment.
 
As with mortality, it is possible that the placebo subgroup will have a higher incidence of cerebrovascular accident. If 2 patients (1 above the expected) in the tranexamic acid subgroup experience a cerebrovascular accident and if 2 or more patients in the placebo subgroup have experienced a cerebrovascular accident, we will continue the study. In this instance, the study will either continue to completion or be stopped if at any point the number of patients with a cerebrovascular accident in the tranexamic acid subgroup exceeds that of the control.
 
If 2 patients (1 above the expected) in the tranexamic acid subgroup experience a cerebrovascular accident and fewer than 2 patients in the placebo subgroup have experienced a cerebrovascular accident, the study will be stopped.
	
age.
 
 
The rate of stroke after hip hemiarthroplasty has been reported to be 0.9% for men and 1.5% for women.
 

Acute Renal Cortical Necrosis	
There is no literature regarding the prevalence of acute renal cortical necrosis following hip hemiarthroplasty. Acute renal cortical necrosis is mentioned as an adverse event that has been spontaneously noted in post-marketing analysis of intravenous use of tranexamic acid.
 
The occurrence of 1 episode of acute renal cortical necrosis in the tranexamic acid subgroup (n = 51) will be sufficient to stop the study for inter-group assessment. If 1 patient (1 above the expected) in the tranexamic acid subgroup experiences acute renal cortical necrosis and if 1 or more patients in the placebo subgroup have experienced acute renal
	

Topical (*Intra-Articular*) Tranexamic Acid and Transfusion Rates Following Hip Hemiarthroplasty

	
cortical necrosis, we will continue the study. In this instance, the study will either continue to completion or be stopped if at any point the number of acute renal cortical necrosis in the tranexamic subgroup exceeds that of the control.
 
If 1 patient (1 above the expected) in the tranexamic acid subgroup experiences acute renal cortical necrosis and no patients in the placebo subgroup have experienced acute renal cortical necrosis, the study will be stopped.
	
Central Retinal Artery/Vein Obstruction	
There is no literature regarding the prevalence of central retinal artery or vein obstruction following hip hemiarthroplasty. Central retinal artery or vein obstruction is mentioned as an adverse event that has been spontaneously noted in post-marketing analysis of intravenous use of tranexamic acid.
 
The occurrence of 1 episode of central retinal artery or vein obstruction in the tranexamic acid subgroup ($n = 51$) will be sufficient to stop the study for inter-group assessment. If 1 patient (1 above the expected) in the tranexamic acid subgroup experiences a central retinal artery or vein obstruction and if 1 or more patients in the placebo group have experienced a central retinal artery or vein obstruction, we will continue the study. In this instance, the study will either continue to completion or be stopped if at any point the number of central retinal artery or vein obstructions in the tranexamic acid subgroup exceeds that of the control.
 
If 1 patient (1 above the expected) in the tranexamic acid subgroup experiences a central retinal artery or vein obstruction and no patients in the placebo subgroup have experienced a central retinal artery or vein obstruction, the study will be stopped.
	

Topical (*Intra-Articular*) Tranexamic Acid and Transfusion Rates Following Hip Hemiarthroplasty

5. *Additional Comments by PI:* The stopping rules were developed based on the available literature regarding complication rates following hip hemiarthroplasty. While rare, complications including death occur in this population following hip hemiarthroplasty. Additionally, these rates vary from study to study. In developing the stopping criteria we used the conservative estimates of adverse events in an effort to prevent overestimating the true rate of occurrence. Using these estimates we considered both the number needed in the tranexamic group to constitute stopping the study as well as the relative difference between the study groups. Given the heterogeneous nature of the patient population and the variability between institutions reporting these events, we may observe a larger number of occurrences in adverse events in both groups. To account for this potential increase in rates across the entire study cohort, the stopping criteria includes comparisons of the number of events between the two groups. Un-blinded data will be reviewed by an independent data safety monitoring board.

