- *Study design:* Double Blinded, Randomized Placebo-Controlled Trial
- *Screening Procedures and who will perform them:*

Patients will be screened for eligibility when they are scheduled to undergo a hip hemiarthroplasty. This cohort consists of patients who present to the emergency department with a femoral neck fracture requiring operative intervention. Screening will consist of a review of the patients' medical history. Prior to screening, verbal consent will be obtained to allow the patient's medical record to be reviewed to determine eligibility. Specifically, patients will be informed about the study by the attending or resident on call and asked whether they are interested in learning more. If the patient is interested, permission for a member of the study team to review their medical record will be sought and documented in the medical record. The information obtained during this screening is also obtained as part of the required work up for patients undergoing operative intervention. If a patient is deemed eligible, they will be offered

Topical (*Intra-Articular*) Tranexamic Acid and Transfusion Rates Following Hip ~~Hemiarthroplasty~~

enrollment into the study and will undergo informed consent. In the event of a screen failure, only year, age, gender, and the reason for exclusion will be recorded on a formal screening log. For screen failures whose age is 90 or greater, the specific age will not be recorded but rather noted as “90+” on the screening log. The PI, Co-Investigator [name], or the orthopedic surgery resident that is on call during the time of admission will be a part of all screening procedures. Each year there is a resident who has one year dedicated to research between their post graduate year 2 and year 3 with time available to dedicated specifically to this project. To ensure that all eligible patients are screened and if appropriate consented, orthopedic surgery residents who take call will be added to the IRB application as consenters following completion of the attached “Educational Plan For Consenters” as necessary. Only those residents with completed training who have been added to the study and have been approved by the IRB will be allowed to obtain consent for study participation.

➤ *Study Procedures and who will perform them:*

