Prior to the start of the study, a randomization schedule will be constructed with block randomization using web-based software. Patients will then be allocated to one of two groups: Topical tranexamic acid or Placebo (saline). Group assignments will be concealed in opaque sealed envelopes with a numerical code of consecutive numbers reflecting patient enrollment. Envelopes will be stored with the pharmacy staff in charge of drug preparation. The pharmacy staff, which will have no patient contact, will remain un-blinded. The pharmacy staff will maintain the master key identifying which patients received the study drug and which patients received the placebo. Physicians, residents, hospital staff, and patients will be blinded to group assignment.

Eligible patients will be offered study enrollment following the screening protocol documented above in the “Screening procedures and who will perform them” section. The PI, Co-Investigator, [name], or the orthopedic surgery resident that is on call during the time of the patients’ hospital admission will obtain informed consent using the informed consent form approved by the IRB. Before a resident can serve as a consenter, he or she must first complete the training protocol found on the form “Educational Plan For Consenters.”

Topical (*Intra-Articular*) Tranexamic Acid and Transfusion Rates Following Hip Hemiarthroplasty

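### Appendix A unblinds surgeon and patient automatically after any listed adverse event, whether or not the allocation is needed for care, which avoidably exposes secondary outcomes in a few patients

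*Combined protocol and SAP*

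**What the plan says.** Section 4 labels the study a "Double Blinded, Randomized Placebo-Controlled Trial". Under the study procedures it states: "Physicians, residents, hospital staff, and patients will be blinded to group assignment". No exception is given there. The pharmacy is the unblinded party: "The pharmacy staff will maintain the master key identifying which patients received the study drug and which patients received the placebo".

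Appendix A, item 2 answers a form question about how adverse events will be dealt with. It says "In the event an adverse event occurs, the surgeon and patient will be un-blinded", and the same sentence goes on to treatment: "will be un-blinded and the patient will be treated according to standard medical practices". The next sentence gives the scope: "Adverse events will include mortality and thromboembolic events". The events named are pulmonary embolism (PE), deep vein thrombosis (DVT), myocardial infarction (MI), stroke, acute renal cortical necrosis and central retinal artery or vein obstruction.

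Two other statements in Appendix A bear on the point. Item 1 says of the intervention, "This is a one-time dose". Item 5 says, "Un-blinded data will be reviewed by an independent data safety monitoring board".

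**The concern.** The rule in item 2 is mandatory. It has no condition that the arm be needed for care, no request step and no record of who was told. It sits beside a blinding statement in Section 4 that has no exception.

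The product is a single application completed before wound closure, so there is no continuing study treatment whose management depends on the arm. Group-level safety review already has its own unblinded route through the data safety monitoring board. An automatic release therefore gives away some allocations that nobody asked for.

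The exposure is what follows the triggering event in the same patient. Transfusion amount, length of stay, complications and inpatient cost are secondary outcomes under the data collection heading of Section 4, and follow-up runs 4 to 6 weeks. The DVT row of the stopping table itself warns that the decision to screen is open to detection bias. After an automatic release, a surgeon who knows the arm would make the remaining decisions on that patient and assess any further event.

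**Working it through.** **The plan's own figure.** A two-sided 0.05 continuity-corrected chi-square with 80% power for 35% v 10% gives 51 per group, 102 in total, as stated in the sample size section.

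**Inputs (Appendix A, item 4 table).** PE 1%; DVT 3% (reported 1.1% to 1.3%); MI 1.9% to 3.1%; stroke 0.1% to 1.5%. Renal and retinal events have no stated rate and are left out. Deaths (102 × 0.0625 = 6.4) are not counted, because a patient who has died has no later decision to bias. Some patients counted below may also die.

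**Patients with PE, DVT, MI or stroke among 102.** The documents do not say how far events overlap, so three assumptions are shown.

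| Overlap | Formula | Low rates | High rates |
|---|---|---|---|
| Full | 102 × largest rate | 102 × 0.030 = 3.1 | 102 × 0.031 = 3.2 |
| Independent | 102 × [1 − product of (1 − rate)] | 102 × 0.0589 = 6.0 | 102 × 0.0834 = 8.5 |
| None | 102 × sum of rates | 102 × 0.060 = 6.1 | 102 × 0.086 = 8.8 |

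With DVT at 1.1% to 1.3%, the lowest value is 102 × 0.019 = 1.9 (full overlap, MI the largest rate). The highest is 102 × (0.010 + 0.013 + 0.031 + 0.015) = 102 × 0.069 = 7.0 (no overlap).

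**In-hospital share.** The documents give no figure. The usual stay is about 3 to 4 days, against 4 to 6 weeks of follow-up. At an assumed 25%, 50% or 75% of 3.1 to 8.8, the patients exposed in hospital number 0.8–2.2, 1.5–4.4 or 2.3–6.6.

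**Further listed events in the same patient.** Under independence, patients with two or more of the four events number 102 × [1 − P(0) − P(1)].
- Low rates: 102 × (1 − 0.94111 − 0.05778) = 0.11.
- High rates: 102 × (1 − 0.91657 − 0.08089) = 0.26.

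Correlated events would raise this. Infection and hematoma, also collected as complications, have no stated rate.

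**Primary outcome.** Expected patients transfused: 51 × 0.35 + 51 × 0.10 = 23, an average rate of 22.5%. Suppose, at the extreme, that every transfusion in an exposed patient follows the event. The first transfusions decided with the arm known are then 0.225 × the in-hospital numbers: 0.2–0.5, 0.3–1.0 or 0.5–1.5. These are decisions exposed, not decisions changed.

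One changed decision moves one arm by 1/51 = 2.0 percentage points, against a planned difference of 25. The continuity-corrected chi-square near the planned rates gives:
- 18/51 v 5/51: p = 0.0045.
- One decision changed towards no difference (17 v 5, or 18 v 6): p = 0.008 or 0.010.
- Two changed (16 v 5, 17 v 6, or 18 v 7): p = 0.014, 0.018 or 0.021.

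The planned result would stand in each case.

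**The case against.** The best reply is that item 2 is a safety exception to a general rule. Section 4 states the general blinding. Item 2 ties unblinding to treatment in one sentence and confines it to serious, named events. That reading is fair, and it is why the two places need reconciling rather than one being discarded. It does not explain why the release is automatic, or why it also applies after death.

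The reply on size also largely stands. The triggering event and any earlier transfusion were recorded blind. The in-hospital share is unknown, and nothing in the documents gives the chance that knowing the arm changes a decision. Repeat listed events are rare under independence. The data analysis section names no between-group test for complications or length of stay, so for those two outcomes no specific planned test can be shown to be distorted.

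A reader might infer three stronger things, and the documents support none of them:

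- **That 6.4 to 15.1 allocations of 102 are compromised.** That count adds the 6.4 expected deaths. Unblinding after death is avoidable but biases no outcome named here.
- **That the primary result is at risk.** The figures above show otherwise.
- **That surgeons would carry the knowledge to later patients, or that the stopping counts would be distorted.** Nothing in the documents shows this. The first listed event in each patient is ascertained before any release.

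Finally, the data collection forms and any separate safety monitoring appendix were not among the documents reviewed. They may contain a code-break procedure, so the absence of a condition can be asserted only of the text available.

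**Conclusion.** The point holds as a minor, inexpensive improvement. As written, item 2 reveals the arm to surgeon and patient without regard to need, in a trial whose main text states blinding without exception. The relevant exposure is the 3.1 to 8.8 patients with PE, DVT, MI or stroke (1.9 to 7.0 at the reported DVT rates).

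For those whose event falls in hospital, the rest of the transfusion amount, stay, cost and complication assessment is open to influence. For events after discharge, mainly the assessment of further complications is left. These counts rest on the planning rates, the stated range of overlap and, for the hospital share, an assumption. No bias in any secondary outcome has been measured.

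**What to change.** Reconcile Appendix A, item 2 with the blinding statements in Section 4:

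- The pharmacy releases an allocation when the treating clinician requests it for that patient's care, and not automatically on the occurrence of an event.
- Each release is logged with date, requester, reason and who was told.
- The number of patients unblinded is reported per arm.
- Events by arm continue to go to the data safety monitoring board.
- Any code-break procedure in the attachments is brought into line with the same text.

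This sets no rule for how any event is treated and does not limit unblinding that the clinician asks for. The cost is one revised sentence, one request step and a short log. The pharmacy already holds the key, and the board already reviews unblinded data.
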